1.2. Rationale

We are running a randomised controlled trial (RCT) to evaluate **the impact of proactive phone calls to residents who are at risk of becoming homeless, signposting them to support services**. We will identify residents as at risk of becoming homeless using Xantura's predictive model. However, this intervention is much lower intensity than the Maidstone model. It signposts to support services, rather than offering support, and is expected to take 20 minutes–1 hour for each household (roughly 30 minutes on average), compared to 8–10 hours per household in the Maidstone pilot.

Unlike the Maidstone Borough Council pilot (Merritt and Davies, 2023), at-risk households in the current evaluation will be randomly assigned to treatment or control groups. This will help us to make a causal inference that any differences

observed between treatment and control are caused by the intervention. We will conduct the trial in four LAs (with individual randomisation of households within LAs) to increase the generalisability of our results. This will also allow us to achieve a larger sample size.

Levels of sophistication in using data and internal analytical capacity are likely to vary between LAs. It is unclear to what extent LAs' data maturity will allow them to adopt and implement data-driven approaches to identifying households at risk of homelessness – and how to use this to target interventions. Therefore, the evaluation also seeks to understand the process of setting up the OneView platform and data sharing, given some of the expected challenges around data governance.

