2. PROJECT SUMMARY

2.1. Project Description

The objective of this project is to evaluate the impact of proactive calls by LAs to households at risk of homelessness, with the aim of preventing homelessness through early and targeted intervention. The early intervention is targeted using the results of a predictive model, but the model is not the subject of the evaluation: the sample will be determined by the model, so both intervention and control groups will have been identified as at-risk by the model; what will differ between groups is whether they are telephoned by the LA. The model uses individual-level as well as household data to identify risk factors (and allow for targeted support at individual level), but the risk levels and factors that are produced as an output are at household-level. The analysis of outcomes will also be conducted at household-level: whether the household has become homeless and is owed a relief duty. A 'household' is the subject of a homeless application; it could refer to an individual as well as a family unit (in any configuration).

The trial will consist of an impact evaluation (IE), accompanied by an Implementation and Process Evaluation (IPE) and an economic evaluation. The intervention will be delivered by four LAs, and their use of the predictive model is being funded by MHCLG. Through the Centre for Homelessness Impact (CHI), MHCLG also funds the independent evaluation of the intervention conducted by Verian.

This project is being conducted as a randomised trial, with households as the unit of randomisation and a household-level outcome measure, with data collection at 2 and 9-months after the end of a 1-month implementation period. The primary outcome measure is whether households are owed a relief duty because they have become homeless. This can happen if a homeless application was made by a household member or by someone on their behalf, and (i) the housing authority assessed the application and accepted that the household was homeless and was owed a 'relief

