any changes made to delivery they observed. Fidelity will be explored in interviews with LA staff and beneficiaries on the basis of the principles set out in the guidance. However, given the number of calls, the inherent flexibility of the intervention, and the scope for differences between LAs, it will not be possible to robustly assess the overall fidelity of the intervention for all participants.

Some LAs may choose to provide more intensive support—more in line with what was offered in the successful Maidstone pilot. Variation in support offered by the LAs will be explored in the IPE, including whether this is a moderator of the success of the intervention.

Table 4: TIDieR Framework

Brief Name: Provide the name or a phrase that describes the intervention	Using Data to Prevent Homelessness: A Randomised Controlled Trial
Why: Describe any rationale, theory, or goal of the elements essential to the intervention	
Evidence shows that there is a clear causal link between financial strain such as financial crises and debt, low income, unemployment and increased risk of homelessness. Debt can also play a role in increasing the length of time that a household experiences homelessness because landlords are reluctant to rent to someone who has high levels of debt or a poor credit report.
 
LAs hold various types of information, such as Council Tax debt, housing benefits, social work data, other housing-related debts, and other vulnerabilities. By combining this data, authorities can identify households at risk of homelessness and direct them to appropriate services. Early identification and support for these households can help manage debts and other needs more effectively, preventing homelessness.

Who (recipients)	Households identified as at risk of homelessness by a predictive model using data collected by LAs. Where identified risk factor(s) pertain to an individual in a household, the individual to which the risk factor(s) pertain will be contacted. Where the risk factor(s) pertain to the household as a whole, any lead adult can be contacted; in the case that the household comprises a couple or more than one lead adult, both/all could be contacted.
What (Materials): Describe any physical or informational materials used in the intervention, including those provided	LA household data, integrated through the OneView data platform.

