3.2. Theory of Change

[figure not shown]

Figure 1: Theory of Change (ToC)

The Theory of Change relies on the following key assumptions:

1. LAs hold all data required by OneView, and a sufficient range of data to allow Xantura to run and deliver a predictive model with meaningful predictive value
2. LAs hold telephone contact information for individuals in identified households, and this information is accurate
3. Contacted individuals can and will answer the telephone, and are able to conduct a long enough call to complete the assessment (in one or across multiple calls)
4. Services that address the needs of the individuals in identified households and can aid in preventing homelessness are available
5. Signposted services have capacity (in addition to BAU workload) to provide meaningful support to individuals in identified households
6. Intervening 3-6 months 'upstream' is early enough to prevent (some) cases of homelessness

The intervention is expected to inform households that they are at risk and refer them to support services that they might need, which (if effective) will also lead to a reduction in homelessness applications (Assumptions 4 and 5 of the ToC).

The causal chain requires households to engage with the services offered by the LA, and for these services to effectively address their needs and reduce household risk of homelessness (Figure 2).

Figure 2: Causal chain for impact on homelessness

Any difference in outcomes between the intervention and control groups is the result of the combination of these two components, engagement and effectiveness. The intervention aims to increase engagement with services; we assume that the effectiveness of these services at reducing household risk of homelessness is constant across intervention and control. Therefore, if we find a difference between intervention and control that will imply that the intervention is effective at increasing engagement with services.

However, if we find a null result, the lack of detectable effect could be because the intervention did not increase engagement with services and/or because the services fail to effectively reduce homelessness. The latter would suggest that LA services need improvement for this intervention to be effective. Whilst these two components (engagement and effectiveness of services) are not measured separately in the

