5.2. Study Design

Study design details

The IE is a two-arm parallel RCT with randomisation at the household level, blocked by LA and predicted risk of homelessness. Households in the 'treatment' arm will receive proactive support (in the form of a phone call) from their LA in addition to BAU support. Households in the 'control' arm will only receive BAU support from LAs. This varies between LAs and refers to the range of activities that LAs and local organisations (including the third sector) undertake, and services they offer, to prevent and reduce homelessness. This support is available to households in both

the intervention and control arms, the difference is whether they receive a phone call that signposts them to the relevant support for them.

Allocation

Verian will randomly allocate households into the trial's two arms with equal probability, with a blocking design to ensure that the sample within each LA is as well balanced as possible on predicted risk of homelessness at the trial's start.

To assign blocks, we will independently sort each LA's sample by a continuous risk score generated by Xantura and then sequentially allocate households to blocks of four, following the sorted order. The target sample size at this point will be a multiple of four, so all blocks should be fully filled. If this is not the case, any remaining households will be entered into the final block. Once sorted into blocks, we will randomly assign households within each block so that every block of four contains two treatment households and two control. If the final block contains an odd number of households, we will randomise those households freely. The sample is thus stratified by LA and then risk score within LA.

We will randomise using the R package 'randomizr' (Coppock, 2019). One researcher will conduct the randomisation, but the code will be checked by another researcher to ensure it has been conducted correctly and can be reproduced. Once conducted, the randomisation code will be saved and made available in the OSF pre-registration that will be published for this trial.

Batching

We will deliver the sample to LAs in three batches, at the start of the first, second, and third months of the trial. We will run the randomisation separately for each batch, using up-to-date risk scores generated by Xantura.

Update to protocol: Study design in Test Valley

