Time Horizon

We will follow CHI's guidance on the evaluation time horizon to ensure consistency with other interventions within the wider Test and Learn programme. In line with that guidance, this economic evaluation will consider all costs and cost savings accruing throughout the time period of the impact evaluation (January 2024 – January 2025).

We will provide estimates of the cost saving unit values (see Table 10 for further details) on a per household / per person per year basis and apply these in line with the evaluation time horizon. Where relevant (and supported by appropriate evidence), we may consider either a shorter or a longer time horizon – e.g. in case of cost savings sustained in the long term. Where this is the case, we will consider a range of plausible time horizons as part of the sensitivity analysis.

In case we find that the intervention costs exceed the cost savings within the core evaluation time horizon, we will include a break-even analysis over time. This will consider a scenario where the intervention is continued on an ongoing basis, applying the intervention to further cohorts of at-risk households over subsequent years. As part of this break-even analysis, we will carry out an assessment out of the level of intervention impacts (in terms of fewer households being owed a relief duty because they have become homeless), intervention costs, and cost savings that would apply in subsequent years of the intervention.

Costs

Costs of delivering the intervention include all of the following: direct costs of the Xantura OneView platform license fee, direct LA costs of staff time spent on setting up the predictive model to identify individuals at risk of homelessness using OneView data platform, direct LA costs of ongoing maintenance and monitoring of the platform, direct LA costs of the preparation and delivery of the intervention phone calls, and indirect LA costs of providing proactive support to members of at-risk households assigned to the RCT treatment group.

Costs of delivering the counterfactual include only the indirect LA costs of providing business as usual support to members of at-risk households assigned to the RCT

control group. If we see significant variation between LAs we will report the range of costs with, where available, information about the factors that seem to drive greater BAU costs.

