Annex B: Call Guidance for Local Authorities

2. Understand their perspective and needs

- a. Using the information provided on Oneview about the individual to start a conversation about potential avenues of support (don't refer specifically to

interactions with the local authority but use the information you have to inform the direction of the conversation/the offers of support)

- i. **If you are satisfied you have completed your needs assessment of the household please enter this in OneView as assessment completed**

- 3. Signpost or complete warm handovers¹⁴ (a warm handover is where you arrange a follow up appointment or directly transfer a person to the team that can offer advice and support) to relevant services - within the buckets
 - a. Financial health
 - i. Debt Advice

Local Services: **ADD IN HERE**
 National Services: Citizens' Advice [contact] (debt helpline) or [Debt Advice - CAB](#), Step Change [contact] [Step Change](#)
 - ii. Welfare Benefits Advice

Local Services: **ADD IN HERE**
 National Services: [Entitled To](#)
 - b. Emotional wellbeing

Local Services: **ADD IN HERE**
 National Service that links to local provision: Call NHS 111 Press 2
[National services: Shout \(text service\) Samaritans Call [name]](#)
 - c. Physical health

Local Services: **ADD IN HERE**
 - d. Housing support

Local Services: **ADD IN HERE**

- 4. Close -
 - a. Ask the person you are talking to if they understand what you have been talking about and if they need anything explaining. Ask them if there is anything that hasn't been covered where they want support.
 - b. Explain what will happen next
 - i. "I have given you the contact details for X and you have said you will contact them" or
 - ii. I have made a referral for you to Y, they will be in touch with you shortly."¹⁵

¹⁴ This will vary from call to call and by local areas. Some people will want to make their own arrangements and in some areas there may not be capacity to complete warm handovers. The outcome is recorded in OneView and this will be taken into account through the evaluation. Warm handovers generally result in improved outcomes for individuals.

¹⁵ London Borough of Barking and Dagenham also plan to use follow up texts 'Dear XYZ, Following your consultation, please see below your personalised care plan. Goals: X Agreed Actions: X Next Steps: X Next Contact Date: X Best wishes, X'

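### The trial is defined as a test of a signposting call, but Section 3.1 permits more intensive support, so a difference between arms need not mean increased engagement

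*Protocol*

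**What the plan says.** **Definition.** Section 1.1 notes that Maidstone's intensity kept that pilot small, and presents this project as a test of a signposting call instead. Section 1.2 says "this intervention is much lower intensity than the Maidstone model" and adds: "It signposts to support services, rather than offering support, and is expected to take 20 minutes–1 hour for each household". The average is put at about 30 minutes, against 8–10 hours in Maidstone. On the contrast between arms, Section 2.1 says "what will differ between groups is whether they are telephoned by the LA" and Section 5.2 says "the difference is whether they receive a phone call that signposts them to the relevant support for them".

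**Permission to do more.** Section 3.1 states: "Some LAs may choose to provide more intensive support—more in line with what was offered in the successful Maidstone pilot". No upper limit follows. Variation in support is left to the process evaluation (IPE), which will ask whether it moderates success. The same section says that overall fidelity cannot be robustly assessed. Annex B, footnote 15, adds: "London Borough of Barking and Dagenham also plan to use follow up texts". The template text sets out a personal care plan with goals, actions and the date of the next contact.

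**Inference.** Section 3.2 says "we assume that the effectiveness of these services at reducing household risk of homelessness is constant across intervention and control". From this it concludes that a difference between arms shows that the intervention raised engagement.

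**Analysis and costing.** The primary model (10.3) has one pooled treatment term. The compliance definition (10.6) does not distinguish a signposting call from fuller support. Section 10.7 plans treatment-by-LA interactions, LA subsample analyses and descriptive work on differential delivery. Section 12.2 counts, among the costs of the intervention, "indirect LA costs of providing proactive support to members of at-risk households assigned to the RCT treatment group".

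**The concern.** The case for the trial is that it tests something lighter and easier to deliver than Maidstone. If an LA gives called households substantially more than signposting, the pooled result describes a mixture: a call in some places, and a call plus added support in others. Two statements could then go wrong. The first is the conclusion in 3.2 that engagement rose. The second is any claim that a low-intensity call produced the effect at its cost per beneficiary household. LAs deciding whether to adopt the call would rely on both.

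**Working it through.** **1. The inference in 3.2.** Let e be the probability that a household engages with services, and s the reduction in risk among those who engage. T is treatment and C is control. The effect is

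e_T·s_T − e_C·s_C = s_C·(e_T − e_C) + e_T·(s_T − s_C).

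The protocol assumes s_T = s_C. The second term then vanishes, and a non-zero effect requires a difference in engagement. If called households receive added support, s_T may differ from s_C, and an effect can arise with e_T = e_C. Engagement may also have risen, but the difference between arms no longer shows that it did.

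**2. The plan's own figure.** Inputs from Section 9: two-sided alpha 0.05, power 0.80, Scenario C with 1,600 analysed (800 per arm), no gain from covariates. The formula is

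n per arm = [1.96·√(2·p̄·(1−p̄)) + 0.84·√(p₁(1−p₁) + p₂(1−p₂))]² / (p₁−p₂)².

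The detectable reduction is 6.98pp at a 50% base rate and 1.97pp at 3%. This reproduces the stated 2–7pp.

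**3. The primary analysis.** Section 5.2 excludes Test Valley, leaving three LAs. At 500 each with 20% attrition, that is 3 × 400 = 1,200, or 600 per arm. The detectable reduction at a 50% base rate becomes 8.05pp.

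**4. Could one LA carry the pooled result?** This is an illustration only. It assumes three equal LAs, no effect in two, and an intention-to-treat effect E in the third, so the pooled effect is E/3.

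| E in one LA | Pooled | Power, 40% base | Power, 50% base |
|---|---|---|---|
| 15pp | 5.0pp | 43% | 41% |
| 20pp | 6.7pp | 67% | 64% |
| 25pp | 8.3pp | 85% | 83% |

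E is limited by reach. Assume that unreached households gain nothing and that reached households carry the base risk. Then E cannot exceed reach × base rate. The only contact rate in the documents is 68 of 210 = 32%, from a different Barking and Dagenham call programme (1.1). At that reach and a 50% base rate, E is at most 0.324 × 50 = 16.2pp, and the pooled effect at most 16.2/3 = 5.4pp, below the 8.05pp in step 3. An E of 25pp needs reach of at least 25/50 = 50%, with every reached case prevented.

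**5. What the LA interaction can show.** Compare one LA (200 per arm) with two (400 per arm), with v = p(1−p):

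detectable difference = 2.80·√(2v/200 + 2v/400).

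This gives 10.3pp at p = 10%, 16.8pp at 40% and 17.2pp at 50%. Even when detected, such a difference cannot be assigned to intensity, because intensity is fixed by LA along with everything else that distinguishes that LA.

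**6. How far apart the two versions are.** With 250 treated households in an LA, 30 minutes each is 125 hours. At 8–10 hours each it is 2,000–2,500 hours, which is 16 to 20 times as much.

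**7. Whether intensity will be recorded.** Table 8 relies on call length and multiple calls from OneView. The list of call-record fields in 11.2 has no call length, and no field for hours or type of support given by the LA itself.

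**The case against.** The discretion is deliberate. Section 3.1 says that LAs would have it at scale-up, and allows follow-up calls for up to six months. On that view, the effect of allocation to an LA-run call is the policy question, and the pooled estimate answers it. Section 10.7 names differences in call handling and in downstream services, and plans LA-level analyses. Sections 11.3 and 12.2 plan case comparisons between LAs and a high–low cost range. Maidstone's officers also helped households engage with other services, so fuller support could work partly through engagement.

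Most of this stands, and it limits the point. It does not reconcile the definitions in 1.2, 2.1 and 5.2 with the permission in 3.1, and it does not rescue the inference in 3.2.

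A reader might infer more than the documents support:

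- **That treatment-arm casework is planned.** Section 3.1 says only that LAs may do it. That the support would go to called households alone is inferred from where the sentence stands and from the costing text in 12.2. Footnote 15 shows follow-up texts, which are compatible with the permitted follow-up calls.
- **That casework in one LA would probably produce the pooled result.** Step 4 shows that this needs a large effect and good reach. The hours in step 6 also sit badly with the limited LA capacity noted in 9.1.
- **That the primary estimate is biased, or that the engagement conclusion must be false.** Neither follows.

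**Conclusion.** The inconsistency is real, and the rule in 3.2 does not hold as written once added support is permitted. The pooled estimate remains a valid effect of allocation to the LA's call list. What is lost is the right to attribute it to increased engagement, or to a low-intensity call alone, if records show that support was added. The LA analyses and the IPE mitigate this only in part, because three or four LAs cannot separate intensity from other LA differences.

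No firm size can be given, since uptake of added support is not in the documents. The figures in steps 4 and 5 rest on assumed equal LA sizes, 20% attrition, base rates of 10% to 50% (40% and 50% in step 4) and a risk-difference scale. Maidstone's reported difference comes from a non-randomised comparison and is not used as an effect size.

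**What to change.** 1. Reconcile Sections 1.1, 1.2, 2.1 and 5.2 with Section 3.1 and Annex B footnote 15 on whether support beyond signposting is part of the tested intervention. No view is taken here on which is right.
2. In 3.2, state that a difference between arms may reflect increased engagement, added LA support, or both.
3. Describe the primary estimate as the effect of allocation to a call run at the LA's discretion, plus any support the LA adds. If records show added support, do not credit the estimate or its cost per beneficiary household to a low-intensity call alone.
4. Add call length to the OneView field list in 11.2, since Table 8 depends on it. Report delivered intensity by LA next to the LA-specific estimates already planned in 10.7, as description and not as a test of moderation.

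The cost is wording and one record field, and Section 13.2 already provides for an addendum before analysis. The downside is a narrower claim about the low-intensity call.
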